### 6.8.3 Expedited Adverse Event Reporting

Expedited AE reporting for this study will be done through the Cancer Consortium IRB and FDA and as required by FDA MedWatch. These requirements are briefly outlined in the table below.

All life threatening adverse reactions reports are submitted to the FDA, our local IRB and to all investigators. A copy of the report is kept on file.

**Table 6.iii.2 Reporting Requirements**

	Unexpected			Expected
	Adverse Reaction (known or suspected attributable to the use of [  F]FES)	AE not attributable to [  F]FES	AE, AR	
	Serious including life-threatening (or death)	Nonserious	Life-Threatening or serious or not serious	Not applicable to [  F]FES
Reporting Time Requirement to the FDA	Report to FDA ASAP and within 7 days of discovery of event (section 6.iii.8.7)	Annual Continuation Review submission	Annual Continuation Review submission	Not applicable to [  F]FES
Reporting Form for the FDA	IND Safety report of potentially serious risk	Annual Reports / Case reports	Annual Reports / Case reports	Not applicable to [  F]FES
Reporting Time Requirement to the local IRB	Report to IRB ASAP within 10 days of discovery of event (suspected is defined as 50% probability attributable to [  F]FES study) this also includes any increased risks with the study even without an AE	At continuation review time	At continuation review time	Not applicable to [  F]FES
Reporting form for the IRB	Expedited Reporting Form for Unanticipated Problems or Noncompliance and Adverse Event Reporting Form	Form for Unanticipated Problems or Noncompliance, Case reports on continuation form, Data Saety Monoring Reports	Form for Unanticipated Problems or Noncompliance, Case reports on continuation form, Data Safety Monitoring Reports	Not applicable to [  F]FES

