## **6.8 ADVERSE EVENTS: LIST AND REPORTING GUIDELINE**

### **6.8.1 Adverse Events and Potential Risks**

No adverse events have been reported for diagnostic [F]FES administration at the strength described for this study in 267 patients studied at the University of Washington. Thus no adverse effects are expected as a result of the administration of [F]FES. The [F]FES dose is less than 0.002 of the recommended safe oral dose assuming an oral conjugated

estrogen dose of 2.5 mg in one day. Unexpected but potential adverse effects are listed below.

Anaphylaxis, Hypotension, Dyspnea, Chest pain, Flushing, Euphoria  
Infection at the injection site or systemic infection  
Extravasation of the dose

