## 6.8.2 Adverse Events Characterization

6.8.2.1 the general definitions for adverse events are:

Adverse Event: Any unfavorable and unintended sign (including an abnormal laboratory finding), symptom, or disease temporally associated with the use of a medical treatment or procedure regardless of whether it is considered related to the medical treatment or procedure (attribution of unrelated, unlikely, possible, probable, or definite). Each AE is a unique representation of a specific event used for medical documentation and scientific analysis.

Serious Adverse Event (SAE): An SAE is defined in the FDA CFR 312 as any adverse drug experience occurring at any dose that results in any of the following outcomes: death, a life-threatening adverse drug experience, inpatient hospitalization, or prolongation of existing hospitalization, a persistent or significant disability/incapacity, or a congenital anomaly/birth defect. Important medical events that may not result in death, be life threatening, or require hospitalization may be considered a serious adverse drug experience when, based upon medical judgment, they may jeopardize the patient or subject and may require medical or surgical intervention to prevent one of the outcomes listed in this definition. We will report serious AEs via expedited reporting to FDA and to our local IRB.

Life-Threatening Adverse Event: Any adverse drug experience that places the patient or subject, in the view of the investigator, at immediate risk of death from the reaction as it occurred, i.e., it does not include a reaction that, had it occurred in a more severe form, might have caused death. AEs can be 'Unexpected' or 'Expected' for expedited reporting purposes only. A list of adverse events that have occurred or might occur (Reported Adverse Events and Potential Risks) can be found in Section 6.8.1.

In addition to oversight by the PIs, this study will be monitored by the UW/FHCRC Cancer Consortium Institutional Review Board and the Radiation Safety Committee.

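### Table 6.iii.2 sets 'suspected' at a 50% probability that is not tied to the five attribution grades and conflicts with the expedited-reporting rules in 6.8.2 and 6.8.3.a

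*Combined protocol and SAP*

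**What the plan says.** Table 6.iii.2 sorts unexpected events by attribution. One group of columns is headed "Adverse Reaction (known or suspected attributable to the use of" FES. Within it, only the serious sub-column is expedited: "Report to FDA ASAP and within 7 days of discovery of event" and "Report to IRB ASAP within 10 days of discovery of event". The local-IRB cell then adds that "suspected is defined as 50% probability attributable to" the FES study. The FDA row has no such definition.

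The only other column for unexpected events is headed "AE not attributable to" FES. It covers events that are "Life-Threatening or serious or not serious" and defers them to the annual submission (FDA) or continuation review (IRB). The column for expected events is marked not applicable, in line with 6.8.1: "Thus no adverse effects are expected as a result of the administration of" FES.

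The text around the table sets other rules:

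- Section 6.8.2 grades attribution on five levels: "attribution of unrelated, unlikely, possible, probable, or definite". It also says that serious adverse events go to the FDA and the local IRB by expedited reporting, with no condition on attribution.
- Section 6.8.3.a requires expedited FDA reporting of on-study deaths whatever the cause, 24-hour reporting of fatal and life-threatening events to both bodies, and submission of every adverse event to the IRB within 10 days.

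**The concern.** Because no FES effect is expected, every event enters the table as unexpected. For a serious event, attribution alone then decides between days and a yearly report. The protocol measures attribution in two ways, a five-level scale and a 50% probability, and never links them. The middle grade, 'possible', is the one left in doubt.

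The safety profile of FES is a secondary objective (6.2.2). Patients have up to three FES injections (6.6.2.g). The repeat scans follow the start of endocrine-targeted therapy, which may be experimental (6.4.1.e, 6.6.2.e), so crediting an event to FES rather than to the other drug can be difficult. Oversight rests on the principal investigators, the IRB and the Radiation Safety Committee (6.8.2). Staff who work from the table could hold back a serious report that the text wants sent promptly, while further injections are given.

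**Working it through.** The 50% is a definition, not a derived figure, so the check is to trace one event through each rule.

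**Step 1: is there a mapping?** Section 6.8.2 gives no grade a probability, and Table 6.iii.2 does not use the grades. The 50% has no direction. It refers to attribution to the FES study, while the column heading refers to use of FES. It is printed only in the IRB row, although 'suspected' stands in a heading shared with the FDA row.

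**Step 2: trace an unexpected, serious event that is not life-threatening (for example, a hospitalisation), graded 'possible'.**

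| Rule applied | FDA | Local IRB |
|---|---|---|
| Table; 'possible' can reach 50% | within 7 days | within 10 days |
| Table; 'possible' below 50%, placed by default as non-attributable | annual | continuation review |
| Table; 'possible' below 50%, columns read strictly | no column | no column |
| Table; 'possible' below 50%, default placement, 50% rule confined to the IRB row | within 7 days if judged suspected | continuation review |
| 6.8.2, serious events | expedited | expedited |
| 6.8.3.a | no rule for this event | within 10 days |

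The same event has several outcomes. No sentence says whether the table or the text governs.

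**Step 3: where does the text stand against the table?** For the IRB there are two statements: the sentence on serious events in 6.8.2 and the 10-day rule in 6.8.3.a. For the FDA, and for events that are serious but not life-threatening, only the sentence in 6.8.2 stands against the table. Fatal and life-threatening events are covered by 6.8.3.a whatever their attribution, yet the table's non-attributable column names life-threatening events and defers them. The conflict is therefore wider than the 'possible' grade.

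**Step 4: scale.** Table 6.4 plans 50 patients. With two or three FES scans each, that is 50 × 2 = 100 to 50 × 3 = 150 injections. Section 6.8.1 reports no adverse events in 267 patients, so the one-sided 95% upper limit is

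1 − 0.05^(1/267) = 0.0112, or 1.12% per patient.

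At that limit, 50 × 0.0112 = 0.56 patients would be expected to have an FES event. This covers events of the kind counted in 6.8.1. It does not bound serious events caused by the cancer or by the endocrine therapy, whose frequency the documents do not give.

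**The case against.** The strongest reply is that the text already protects these reports. Section 6.8.3.a sends all adverse events to the IRB in 10 days, and 6.8.2 expedites serious ones to both bodies, directly after a definition that includes hospitalisation. Section 6.8.3 presents the table only as a brief outline. 'Possible' is not the same as 'not attributable', so the table is silent on such events and does not expressly defer them. The FDA row carries no 50% rule. The IRB cell also takes in any increased study risk, even without an adverse event. Finally, the threshold may reflect local IRB policy, which cannot be checked here.

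Most of this stands, and it defeats a stronger reading. A reader might infer that the protocol sends a serious, possibly related event to annual reporting only, with a delay of about 12 months. That follows only from the table read alone, with 'possible' taken as under 50% and placed by default in the non-attributable column. The documents state neither step, and the text contradicts the result. A reader might also infer that a first FES reaction would usually be graded 'possible' and rarely reach 50%. Nothing supports this. Several of the risks listed in 6.8.1, such as anaphylaxis, are acute, and such events close to an injection could well be rated 'probable'.

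The reply does not remove the conflict. If the text governs, the 50% definition and the deferral of serious events have no function. If the table governs, it narrows the text. Calling the table an outline does not say which prevails.

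**Conclusion.** The point holds as an inconsistency in the reporting rules. The 50% definition has no direction and no link to the 6.8.2 grades, and its reach to FDA reporting is unclear. Serious 'possible' events have no clear column, and the table conflicts with 6.8.2 and 6.8.3.a without a stated order of precedence. Annual-only reporting is not the settled result of the whole protocol, but the table permits it.

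For the events affected, the difference is 7 days (FDA) or 10 days (IRB) against up to about 12 months. The placement of 'possible' rests on the assumption that it means under 50%. The conflict over serious events in the non-attributable column does not need that assumption. Few FES-related events are likely in 50 patients. No endpoint, power or sample size changes. The correction is still worth making, because it concerns prompt safety reporting and costs almost nothing.

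**What to change.** Reconcile Table 6.iii.2 with 6.8.2 and 6.8.3.a:

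1. Remove the 50% definition or make it consistent with the text. If it is local IRB policy, limit it explicitly to that row and state that the stricter text governs.
2. Word the attribution columns in the five grades of 6.8.2, so that serious events graded 'possible', 'probable' or 'definite' fall in the expedited column for both the FDA and the IRB.
3. Correct the non-attributable column so that it no longer defers serious or life-threatening events against 6.8.2 and 6.8.3.a. Editing only the 'possible' grade would leave that conflict in place.

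The cost is an edit to one table, with a sentence on precedence if the threshold is kept. The downside is possibly a few more expedited reports. Step 4 of the working suggests that few would come from FES itself. The number from unrelated serious events cannot be derived from the documents, but 6.8.2 already asks for those reports.

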### **6.8.3.a Expedited Reporting Guidelines**

All deaths for subjects while on study will be reported to FDA using expedited reporting regardless of causality. Attribution to treatment or other cause will be provided.

Fatal and life-threatening events will be reported to the University of Washington IRB within 24 hours of notification of the event, indicating that a full report will follow. All adverse events will be submitted to the IRB within 10 days of notification of the event.

Fatal and life-threatening events will also be reported within 24 hours to the FDA following the MedWatch guidelines set by the FDA in compliance with the 21 CFR 312.32.

Life-threatening (or fatal) adverse reactions must be reported within 7 days to the FDA. The FDA should be notified as soon as the adverse reaction is discovered by telephone or fax or email. The instructions and forms are available at <http://www.fda.gov/Safety/MedWatch/HowToReport/default.htm>. The report should be sent ASAP by mail and followed with a follow-up report. Individual IND safety reports to FDA are submitted on the Medwatch FDA Form 3500A as an "IND Safety Report". The form should be sent to The Director, Office of Generic Drugs in the Center for Drug Evaluation and Research at FDA. The address and phone numbers are available at: <http://www.fda.gov/AboutFDA/CentersOffices/CDER/ucm119100.htm>.

## **6.9 PHARMACEUTICAL INFORMATION**

### **6.9.1 Production of the Radiopharmaceutical**

[F]FES will be produced at the University of Washington according to the methods described in Section 7 of this IND application, Chemistry, Manufacturing and Controls.

### **6.9.2 Reported Adverse Events and Potential Risks:**

A list of the adverse events and potential risks associated with [F]FES was provided in Section 6.8.1.

### **6.9.3 Agent Accountability:**

The chemical precursor for [F]FES is provided in house or by ABX in single-use, 2 mg vials that are delivered to the custody of [name], the lead radiochemist for this project. They are stored in a controlled temperature freezer in a locked and secure room and they are

inventoried with a chain of custody maintained from the time of receipt. Each radiosynthesis is done by [name] or his designee and, after passing all required quality control assays, the product [F]FES dose is drawn up under the supervision of the nuclear medicine physician investigators, [name], [name] or [name]. The quality control tests that must be passed prior to release of the product [F]FES for injection include the pH, radioactive purity, radiochemical purity, specific activity, sterilizing filter integrity, tests for Kryptofix [2.2.2], acetonitrile, endotoxins and particulates. Acceptance criteria are detailed in the CMC document. The [F]FES dose is drawn up into a syringe, assayed for mCi at time of injection, labeled and administered to the research subject.

## **6.10 CORRELATIVE/SPECIAL STUDIES**

### **6.10.1 FDG-PET Imaging**

In most cases, a standard clinical diagnostic FDG PET or PET/CT scan will be obtained prior to the [F]FES PET scan. The FDG PET or PET/CT scan serves to help identify active sites of breast cancer and is used to help determine sites on the FES PET scan where estradiol binding would be expected. At least one site of measurable disease outside of the liver, where quantification of FES uptake can be difficult because of normal biodistribution, must be evident on the FDG PET scan and CT or MRI. FDG PET imaging will be completed close to the time of the FES PET scan. In select cases where the baseline FDG PET is being repeated at our institution for the purposes of this study it may be completed after the FES PET. The FDG PET will be a clinical 5 axial field-of-view (AFOV) scan from skull base to mid-thigh. Maximum SUV of identified lesions will be calculated and recorded as per standard clinical procedure.

For FDG PET or PET/CT, all patients will fast for at least 4 hours before PET scanning. All patients must have a medical history negative for diabetes and/or a pre-scan serum glucose level less than 200 mg/dL. A dose of 260-370 MBq (7-10 mCi) of FDG will be injected into a peripheral intravenous or central venous catheter. Patients will rest comfortably in a supine position prior to scanning. Imaging will be performed with a commercially made PET/CT scanner operating in the high sensitivity mode. Imaging will consist of a torso survey covering five adjacent 15-cm axial fields of view (FOVs). For the PET/CT device, a low dose CT scan beginning at approximately 60 minutes after FDG injection provides attenuation data for attenuation correction using a non-contrast CT. Emission data will be collected for all five axial FOVs, typically five minutes per FOV.

Emission data will be reconstructed according to standard protocols. Images will be corrected for radioactive decay of the tracer and normalized to the injected dose and body weight, which results in regional standardized uptake values (SUVs): as defined in section 6.10.3.

We emphasize that the baseline FDG PET or PET/CT is part of standard clinical care of metastatic and recurrent breast cancer and will be performed as part of routine clinical care in the vast majority of patients participating in the study. Methodology for FDG PET is included in this section for reference purposes. In some cases, FDG PET or PET/CT will have already been performed at an outside center at the time of enrollment. On rare occasions when patients have been referred to the study with a recent FDG PET scan already completed at an outside site that is unavailable or of insufficient detail for our study, or the patient is unable to obtain a PET scan as part of standard clinical management, we will repeat the FDG PET at the University of Washington as a research scan, however, the imaging procedure will not vary from that of a standard clinical scan.

Patients will undergo a second (and potentially a third in a subset of patients) FDG PET following the same imaging procedure as part of the research study. This second scan will be performed at a time point stipulated by the treatment regimen and may vary from 1 to 12 weeks post therapy start.

## **6.10.2 [F]FES-PET Image Assessment**

### **6.10.2.a Summary of Assessment**

The FES PET scan will be assessed in multiple ways.

Qualitative FES uptake: all known disease sites positive vs. heterogeneous or absent FES uptake.

Quantitative FES uptake: SUVs in all lesions measured at baseline and repeat scan (and at third scan if indicated)

Quantitative change in FES uptake: percentage and SUV unit change in SUV between baseline and repeat FES PET scan

### **6.10.2.b Qualitative Visual Assessment**

Qualitative (visual) assessment of level of uptake in sites of recurrent breast cancer is performed for all studies. In this analysis, trained observers determine whether FES uptake is present above background at

sites of breast cancer. Active disease sites are identified by the FDG PET scan performed close to the time of FES PET, in conjunction with conventional imaging such as CT, MRI, and bone scan. Active sites of disease are defined as sites with (1) abnormal uptake on FDG PET and (2) either biopsy confirmation or unequivocal correlative findings on at least one other modality. For each site of active disease, two trained observers blinded to the clinical data, but with any available FDG PET and correlative imaging, will determine whether FES above background levels is present or absent. Differences between observers will be resolved by consensus.

#### **6.10.2.c Quantitative Assessment**

FES static survey images will undergo region of interest (ROI) analysis as follows: Lesion location will be identified using FES scans along with FDG scans with reference to CT or ultrasound. All patients will have undergone clinically motivated FDG PET scans for staging prior to FES imaging. CT, MRI, ultrasound or bone scan will be available on all patients with suspected metastatic disease. Although FES and FDG imaging will be performed on separate days, studies will be performed with the patient in the same position and images will be co-registered using common anatomic landmarks such as the lung outline, cardiac blood pool, liver contour, and body outline. In this way, regions can be drawn on the FDG images and transferred to the FES images for quantitative analysis which is important in identifying tumor locations, especially in ER-negative tumors which are not visualized on FES imaging. For each disease site, a set of 1.5 cm diameter regions on three adjacent planes with the highest lesion FES uptake will be drawn to determine maximal FES uptake. Up to the 10 largest sites seen on the static torso survey will be quantified. Partial-volume correction will not be used because only sites 1.5 cm or greater diameter will be included in quantitative analysis.

FES uptake will be quantified using the standard uptake value (SUV, defined below). For each site, we will record the average and maximum SUV within the ROI set for each site of disease.

For each subject, we will calculate the average and range of FES uptake values for active disease sites. The FES uptake will be compared with subsequent response to endocrine therapy and TTP.

FDG studies will also be quantified for uptake in a similar fashion. On FDG studies, simple SUVs will be generated using the average tissue activity over the imaging period, which are typically 45 and 75 minutes after injection. We will record the maximum FDG SUV for each site of

disease. Uptake at tumor sites using the standardized uptake value (SUV) is calculated as:

$$SUV = \frac{\overline{C}_t}{ID / wt}$$

where  $\overline{C}_t$  is the average tumor uptake after injection for the period of the static imaging for torso surveys (MBq/mL), ID is the injected dose (GBq) and wt is the patient's weight (kg). Note that either standard or metric units can be used to calculate SUV as long as only one type of unit is used for each calculation.

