## **6.4 PATIENT SELECTION**

### **6.4.1 Inclusion Criteria:**

- 6.4.1.a** Adult, non-pregnant patients with biopsy-proven or clinically obvious primary, recurrent or metastatic breast cancer
- 6.4.1.b** Breast cancer from ER+ primary that is seen on other imaging tests. Tumor ER expression must have been confirmed by immunohistochemistry of primary tumor or recurrent disease.
- 6.4.1.c** At least one site of disease 1.5 cm or greater is needed to meet the spatial resolution limits of PET imaging.
- 6.4.1.d** Patients must have been off tamoxifen or other estrogen receptor blocking agents for at least 6 weeks and off chemotherapy for 3 weeks for the initial baseline FES.
- 6.4.1.e** Patients must be selected for an endocrine targeted therapy regimen for treatment of their breast cancer by the referring oncologist. Selected treatments may be part of experimental treatment protocols for which the patient would be separately consented.
- 6.4.1.f** Patients must be willing to undergo serial imaging procedures.
- 6.4.1.g** Patients must agree to allow access to clinical records regarding response to treatment and long term follow up.

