## **6.14 STATISTICAL CONSIDERATIONS**

### **6.14.1 Analysis Plan**

The primary application will be pilot studies with enrollment of about 20 patients, in which the in vivo effects of endocrine-targeted therapy are measured by serial FES PET. The primary endpoints will be quantitative and qualitative measures of FES uptake, and measures of change in FES uptake (Section 6.10.2). Additionally, patients will be followed for disease progression. Associations among FES and FDG PET measures, progression, and biological correlates (Section 6.10.3) may be examined in descriptive analyses.

An expected primary analysis is to examine whether FES uptake changed on average between serial assessments. This may be assessed by a one-sample test of the percent change in FES SUV. For example, a one-sided test at the 0.05 level of significance could evaluate whether the average

percent change in FES SUV was greater than 20%, considered a biologically significant change. In serial FES SUV measurements of heavily-pretreated breast cancer patients, change in FES SUV was approximately normally distributed with a standard deviation of about 25 percentage points, for both patients treated with blocking therapy (tamoxifen or fulvestrant) or non-blocking therapy (aromatase inhibitor). Using this standard deviation and n=20 to test whether the average change was greater than 20%, the power would be 0.97 if the true change is 40%, and 0.85 if the true change is 35%. To conclude only that the average percentage change was different from zero (using a two-sided test at the 0.05 level of significance), power would be 0.95 to detect a true average change of 20% (and 0.85 if the true standard deviation were 30 percentage points).

Other analyses for pilot studies could examine what proportion of patients experienced a threshold in percentage change, or surpassed a targeted follow-up FES SUV value. These percentages will be reported using a 90% Wilson score binomial confidence interval (Agresti, 1998). Width of these confidence intervals for pilot studies of n=20, n=25, and n=30 are given in Table 6.3 for a range of observed percentages.

**Table 6.3:** 90% Wilson score binomial confidence intervals (CIs) by percent observed and sample size.

observed percentage (CI) for n=20	observed percentage (CI) for n=25	observed percentage (CI) for n=30
0.1 (0.03, 0.26)	0.12 (0.05, 0.27)	0.1 (0.04, 0.23)
0.2 (0.09, 0.38)	0.20 (0.10, 0.36)	0.2 (0.11, 0.34)

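### The 1.5 cm size floor does not justify omitting partial-volume correction: measured FES SUV still depends on lesion size, so shrinkage can add to the apparent decline

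*Combined protocol and SAP*

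**What the plan says.** Section 6.10.2.c gives one reason for leaving out the correction: "Partial-volume correction will not be used because only sites 1.5 cm or greater diameter will be included in quantitative analysis". The same paragraph sets the measuring region: "a set of 1.5 cm diameter regions on three adjacent planes with the highest lesion FES uptake will be drawn to determine maximal FES uptake". For each site, "we will record the average and maximum SUV within the ROI set for each site of disease". No section says which of the two feeds the primary percent change.

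Inclusion criterion 6.4.1.c uses the same size: "At least one site of disease 1.5 cm or greater is needed to meet the spatial resolution limits of PET imaging". No resolution (FWHM) is stated anywhere.

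Section 6.10.2.a defines the change endpoint as "percentage and SUV unit change in SUV between baseline and repeat FES PET scan". Section 6.14.1 offers a one-sided 0.05-level test of whether the average "percent change in FES SUV was greater than 20%, considered a biologically significant change", and a two-sided 0.05-level test against zero. It also allows for reporting the proportion of patients who pass a percent-change threshold or reach a target follow-up SUV.

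The repeat scan typically falls 1-12 weeks into therapy (6.6.2.e). Section 6.12 plans no response evaluation within this study. I found no adjustment for lesion size, and no statement on whether the 1.5 cm floor applies again at the repeat scan.

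**The concern.** A minimum size can make a lesion measurable without making its SUV independent of size. PET blurs a lesion into its surroundings, and a 1.5 cm region on a 1.5-2 cm lesion averages over that blurred edge. The loss cancels in a percent change only if the lesion is the same size on both scans. Here the second scan follows treatment that may shrink the tumour, and a smaller lesion then reads lower with the same true uptake.

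Sections 6.2.1 and 6.3.3 read the change as an effect on ER expression or estradiol binding. Part of an observed decline could instead be geometry. With no lesion diameters recorded for analysis, that part could not be separated afterwards. Both the test of the mean change and the patient-level threshold proportions are exposed.

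**Working it through.** **1. The plan's own power figures.** Inputs from 6.14.1: n=20, SD 25 (30 as the alternative). SE = 25/√20 = 5.590, and power = Φ(δ/SE − z).
- True 40% against 20%, one-sided: Φ(20/5.590 − 1.645) = Φ(1.933) = 0.973 (plan 0.97).
- True 35% against 20%, one-sided: Φ(15/5.590 − 1.645) = Φ(1.038) = 0.850 (plan 0.85).
- True 20% against 0, two-sided: Φ(3.578 − 1.960) = 0.947 (plan 0.95).
- The same with SD 30 (SE 6.708): Φ(2.981 − 1.960) = 0.846 (plan 0.85).

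All four reproduce, so the same formula is used in step 3.

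**2. Effect of size on one lesion.** From 6.10.2.c: 1.5 cm circular regions on three adjacent planes. Assumed, because the documents do not give them: uniform sphere, centred region, planes 4 mm apart, lesion SUV 4, background 1, Gaussian blur of 5-10 mm FWHM. Let RC be the mean (or maximum) over the region of the blurred unit sphere. Measured SUV = 1 + (4 − 1) × RC.

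At 15 mm, the average-based RC is 0.61, 0.46 and 0.37 at FWHM 5, 8 and 10 mm. At the floor, 39-63% of lesion contrast is lost.

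Example at FWHM 8 mm: RC is 0.744 at 20 mm and 0.520 at 16 mm, so SUV goes from 1 + 3×0.744 = 3.23 to 1 + 3×0.520 = 2.56, a fall of 21%.

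Apparent fall with unchanged uptake, at FWHM 5 / 8 / 10 mm:

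| Diameter | Region average | Region maximum |
|---|---|---|
| 20 to 16 mm | 18 / 21 / 22% | 0 / 8 / 15% |
| 20 to 15 mm | 24 / 27 / 27% | 0 / 11 / 20% |
| 25 to 20 mm | 7 / 14 / 17% | 0 / 2 / 8% |
| 30 to 24 mm | 1 / 7 / 11% | 0 / 0 / 3% |

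Both diameters in every row are at or above the floor. Background matters: varying it from 0 to 0.33 of lesion uptake (planes 3.5 mm apart) widens the 20 to 15 mm range to 20-41% for the average and 0.4-28% for the maximum.

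**3. Effect on the trial-level tests.** Suppose true uptake is unchanged and the mean artefact is m points. The zero-change test rejects with probability Φ(m/SE − 1.96) + Φ(−m/SE − 1.96). The greater-than-20% test rejects with probability Φ((m − 20)/SE − 1.645).
- m = 5: 0.15, and below 0.001.
- m = 10: 0.43, and below 0.001.
- m = 15: 0.77, and 0.006.
- m = 20: 0.95, and 0.05.

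For scale, 6.3.3.c reports objective response in 11/47 (23%) over 6 months. If only that fraction of patients lost 25% by artefact, m = 0.23 × 25 = 5.75, and the zero-change test rejects with probability 0.18. If they lost 38%, m = 0.23 × 38 = 8.7 and the probability is 0.34. In both cases the greater-than-20% test rejects with probability below 0.001.

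**The case against.** The strongest reply has five parts.

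- **Meaning of 1.5 cm.** A reader might infer from 6.4.1.c that the scanner resolves only 1.5 cm. The text does not say so. It gives 1.5 cm as the smallest adequate lesion. This stands, and the calculation above assumes 5-10 mm instead.
- **Choice of SUV.** The region is drawn to find maximal uptake, and maximum SUV is much less affected: none of the tabulated pairs exceeds 20%. This stands in part. The plan records both statistics and does not name the primary one.
- **Lesion against group.** The 20% margin applies to the average across patients, and 6.10.2.c also averages sites within a patient. A reader might infer that shrinkage alone could carry the trial past that margin. The documents do not support this. It would need nearly every patient to have small, shrinking sites, whereas 6.3.1.c puts response at 7-21% in pretreated recurrent disease and repeat scans come early. Section 6.3.3.e reports an average decline below 15% on aromatase inhibitors. That does not exclude a bias of 5-10 points, and the trial also admits primary tumours. For new diagnoses, 6.3.1.c cites 30-77% response.
- **Link to outcome.** A reader might also infer a false association between FES change and response. An artefact concentrated in shrinking tumours could act that way, but such associations are only descriptive in 6.14.1. This is secondary.
- **Feasibility.** The attenuation CT is low-dose and non-contrast, some scans may be PET only, and the calendar lists no diagnostic CT at repeat. This limits how many lesions can be sized. However, the plan must already size sites to apply its floor and choose the 10 largest.

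**Conclusion.** The concern holds in limited form. The reason given in 6.10.2.c does not support omitting the correction, because a 1.5 cm region on a lesion near 1.5-2 cm gives an SUV that varies with size. For single lesions, shrinkage from 20 mm to 15-16 mm could mimic a decline of about 18-27% in region-average SUV, or about 0-20% in maximum SUV. Lesions of about 3 cm are little affected. At trial level the exposure is mainly in the two-sided zero-change test, whose error rate would be about 0.15-0.43 under a mean artefact of 5-10 points, and in the patient-level threshold proportions. A 20-point average artefact is not shown, and at the artefact sizes considered plausible here the greater-than-20% test is not inflated.

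The lesion figures rest on resolution, contrast, geometry and amount of shrinkage that the documents do not give. The trial-level figures rest on the plan's n=20 and SD 25, with an assumed mean artefact.

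**What to change.** 1. Delete the stated justification in 6.10.2.c, and state the scanner resolution.
2. Name the SUV statistic for the percent change. Make maximum SUV, or a small peak region, the primary or a co-reported measure, because it depends less on size.
3. State that a site eligible at baseline stays in the paired analysis if it falls below 1.5 cm at repeat. Otherwise the lesions that shrink most would drop out.
4. Record each quantified lesion's diameter at each scan where the existing PET/CT or correlative imaging allows.
5. Pre-specify a sensitivity analysis of the percent change by lesion size (for example, baseline diameter below against at or above about 2.5-3 cm) or by change in size. Recovery correction can be optional for measurable soft-tissue lesions.
6. Report how consistent the decline is across lesion sizes when interpreting it as an ER effect. Requiring it to hold in large or corrected sites before calling it an ER effect would be too strict for a pilot of about 20 patients.

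Cost: one extra measurement per lesion and one sensitivity analysis. Maximum SUV is noisier, the large-lesion subset will be small, and bone lesions or PET-only scans may have no usable diameter.
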